## 7 MANAGEMENT OF ADVERSE EXPERIENCES

Expected side effects include those observed in the prior adult/adolescent phase 2b trials in FXS and the pediatric PK study. These include dizziness, insomnia, headache, decreased appetite, vomiting, diarrhea, and behavioral “activation” with irritability, aggression, hyperactivity, anxiety, and impulsive behavior. These side effects are expected to be relatively infrequent, mild-moderate in degree, and insomnia and other side effects will in most cases be identified in the flexible dosing period and managed by dose adjustments during the flexible dosing period.

Insomnia may be managed by moving the dose from evening to afternoon as early as 3 PM, though doses must remain at least 4 hours apart. If the subject's dose is reduced to 12.5 mg BID during the flexible dosing period and the subject still has intolerable side effects, that subject will be withdrawn from the study. This is not expected to occur frequently based on past experience with AFQ056 in the above-noted studies. Subjects requiring dose reduction for presumed side effects after the flexible titration when the dose is to remain fixed in the placebo-controlled period (between the 2 and 8 month visits) will be withdrawn from the study. Dose reductions for side effects during the fixed dose period of the open label extension will not be encouraged but may be allowed after review of the situation.

No clinically significant laboratory or EKG abnormalities have been seen in other studies of AFQ056 outside of non-drug related abnormalities that may have occurred during intercurrent illness. If laboratory or EKG abnormalities that are deemed to be clinically significant by the site investigator occur, these can be repeated and if still abnormal will require specific follow up testing depending on the nature of the abnormality and medical standard of care for the type of

AFQ056 for Language Learning in Children with FXS

Version v15

Version date 02/03/2021

abnormality observed. The subject may be withdrawn from the study depending on investigator and medical monitor assessment of likelihood of relationship to the study treatment with AFQ056.

Adverse events seen in the prior adolescent and adult placebo-controlled studies of AFQ056 in FXS more frequently in the group treated with AFQ056 than with placebo include the following list arranged in alphabetical order. No side effect exceeded a frequency of 20%, even at the highest doses of AFQ056 (see section 2.2 above for exact frequencies). In the Pediatric PK study, side effects all fell into the below categories, with vomiting and insomnia being the most frequent side effects. These were typically short-lived occurring in the first day or two of dosing and seemingly related to advancing to the full dose right from the outset of doing rather than titrating the dose up over time. This was evident in that vomiting after the initial dose was seen in 50% of the 5-11 year old cohort studied first all of whom were dosed from the outset at the full dose, but not seen in the 3-4 year old cohort after dosing was advanced over the course of a day (half dose for one day, followed by the full dose).

- Abdominal pain
- Agitation
- Aggression
- Anxiety
- Decreased appetite
- Diarrhea
- Dizziness
- Fatigue
- Headache
- Insomnia
- Irritability
- Nausea
- Pyrexia
- Self-injurious behavior
- Vomiting

Although not seen in prior trials in humans with FXS, including after AFQ056 exposure for over two years in the open-label extension studies with adults and adolescents (2278 and 2279), learning and memory impairment have been noted in preclinical testing of AFQ056. Learning was, however, enhanced in preclinical testing in the FXS mouse model, presumably due to the AFQ056 targeting the abnormal signaling pathway in the FXS mouse. Risk of learning and memory impairment will be monitored closely using assessments that are being administered as part of the protocol. Raw scores on the MSEL and VABS-II assessments will be monitored at the sites to assess global developmental functioning. If there is a decrease in raw scores on both measures by 10% incrementally at two consecutive visits where both assessments are administered (e.g. 10% decrease from screening to baseline, baseline to month 2, month 2 to month 8, or month 8 to month 16 as described in the schedule of assessments), subject data will be reviewed by the Medical Monitor and it will be decided if the subject should be withdrawn from the study. If there is decrement in these scores without any obvious alternative cause the participant will be withdrawn from the study.

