
The majority of males with FXS will meet criteria for mild to severe intellectual disability. Average IQ in adult males with FXS is 40-50. Females with FXS are often less affected than males with about 25% having cognitive impairment and others frequently being diagnosed with learning disabilities. Average IQ in females is about 80, with a range from severe impairment to normal or even superior ability. Multiple studies have shown a decrease in full-scale IQ scores and adaptive behavior with age as children with FXS become older.. Decline in standard scores for intelligence and adaptive function is not the results of loss of skills or regression but rather failure to keep pace with the normal rate of intellectual development. Behavioral dysfunction is very commonly seen in FXS and includes attention deficits/hyperactivity, hyperarousal, anxiety,

perseverative behavior and aggression. About a 50-67% of males and about 20% of females with FXS meet criteria for ASD. Although psychopharmacologic treatment for behavioral symptoms (with stimulants, SSRIs, antipsychotics depending on most problematic symptoms) is often employed in FXS, these medications are incompletely effective likely due to the environmental contingencies maintaining the behaviors, and there are no treatments for the underlying cognitive disorder. **Thus, treatment of both behavior and cognition/development in FXS represent areas of high need.**

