After 8 month assessments in the placebo-controlled phase (including 6 months of language intervention), all subjects will enter the extension and be treated with active drug according to the same schedule as in the placebo-controlled phase. All subjects will be dosed with 25 mg BID of unblinded AFQ056 upon completion of the 8 month visit, followed by 2 months of flexible dose forced-titration to the MTD of the dose levels available in the protocol (dose adjustments to be done as described above for the placebo-controlled period for the flexible dose forced-titration). This will be followed by a period of stable treatment. The length of stable treatment will be dependent upon how long after June 15, 2019 the participant enrolls and what dose of drug they are receiving in the open label treatment period. The total duration of the stable treatment for those enrolled after June 15, 2019 will range from 6 months to no open label extension, depending on the number of months after June 15, 2019 the subject is enrolled into the study.

Some subjects will have an acute dose decrease if they were on 50-100 mg BID of active drug in the initial phase but experience from the PK study suggests that children can come off AFQ without withdrawal symptoms and the dose decrease and titration in the open label extension are unavoidable to maintain the blind of the study through the completion of the placebo-controlled period by the final participant. Subjects will continue the language intervention through the extension phase. The open-label extension will allow all children a period of active drug exposure to make recruitment feasible, despite the long placebo period. It will also allow an assessment of more long term-effects of the language intervention and its impact on the ERP and eye tracking biomarker outcomes and other developmental and behavioral outcomes, will allow examination of the trajectory of the language intervention going from placebo to drug treatment in a blinded setting, and will furthermore allow additional long-term safety data to be collected on a larger cohort of children exposed to AFQ056. A diagram of the study design is provided below in Figure 2.

Figure 2. Effects of AFQ056 on Language Learning in Young Children with Fragile X Syndrome (FXS) – Protocol Design

AFQ056 for Language Learning in Children with FXS

Version v15

Version date 02/03/2021

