## **6.2.3 Study Medication/Intervention Discontinuation Evaluations/procedures**

Study medication/intervention discontinuation will occur when subjects complete the study or withdraw from the study early (after randomization). At study completion, subjects will complete all the assessments and procedures for the 16 month visit (visit 14).

If a subject withdraws from the study after randomization, a Termination visit should be conducted as soon as possible. The assessments and procedures completed during the termination visit will depend upon whether the subject discontinued study drug prior to the termination visit. Assessments and procedures are to be completed as possible based on agreement of the caregiver at the termination visit(s) as follows:

- The subject is on study drug at the time of the visit
  - The termination visit will include all the assessments and procedures for the 16 month visit (visit 14).
- The subject discontinued study drug prior to the visit
  - The termination visit will include the following safety assessments and procedures
    - Blood draw
    - Urine dipstick
    - EKG
    - Vitals
    - Physical, neurological and psychological exams
    - Suicidality assessment
    - Fundoscopic exam

- AE review
- Study drug accountability

A follow up visit after the Termination Visit with the subject off study drug should be conducted 30 days after the termination visit.

Study medication will be weaned over 1-2 weeks for subjects on a dose of >25 mg BID AFQ056 or placebo, and stopped without weaning for subjects on a dose of 12.5 or 25 mg BID. For participants on a dose of 50 mg BID, the dose will be weaned to 25 mg BID for a week and then stopped. For participants on 75 mg BID or 100 mg BID, the dose will be weaned to 50 mg BID for a week and then to 25 mg for a week, and then stopped.

Discontinuation criteria for individual subjects are listed in section 4.3 of the protocol – please refer to that section for more details.

The entire trial will be stopped if 3 serious adverse events considered probably or definitely due to drug occur or upon recommendation by the DSMB based on unblinded review of adverse events.

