## 9.6 Statistical Analysis Plan

### 9.6.1 Primary Hypothesis

**Primary Efficacy Hypothesis:** *Children treated with AFQ056 will show greater improvement in language and its nonverbal communicative precursors as reflected in on change in a weighted communication score designed to assess both the proclivity to engage in communication and the sophistication of the means employed for communication from baseline (visit 3 assessment) to 8 months (visit 9 assessment) than those treated with placebo.*

The study design is longitudinal involving unequally spaced data collections over the placebo-controlled phase at 0 (baseline), 2, 4, and 8 months (see Figure 2). Focus is on the difference in the rate of change among the placebo (PL) and treatment (TX) groups. To account for the model design and potential dropout, linear mixed models (LMMs) will be used for the analysis.

Suppose that  $Y_{ij}$  is the outcome (e.g., language score) for the  $i^{\text{th}}$  participant ( $i = 1, \dots, N$ ) at the  $j^{\text{th}}$  time point ( $j = 1, \dots, T_i$ ). Assuming linear change over time, the LMM can be written as:

$$Y_{ij} = \beta_0 + \beta_1 t_{ij} + \gamma_0 g_i + \gamma_1 t_{ij} g_i + (b_{0i} + b_{1i} t_{ij} + e_{ij}) \quad (1),$$

where  $g_i = 1$  if the participant is in TX and 0 if in PL,  $t_{ij}$  is time in months,  $b_{0i}$  and  $b_{1i}$  are random effects,  $e_{ij}$  is random error, and the remaining parameters are fixed effects. We make the typical normality and related assumptions for the random effects and random error. Due to randomization, there is no average intercept difference and we set  $\gamma_0 = 0$ . The mean longitudinal change is then: for PL is then:

$$\text{For PL: } E(Y_{ij})_{\text{PL}} = \beta_0 + \beta_1 t_{ij} \quad (1a),$$

$$\text{For TX, } E(Y_{ij})_{\text{TX}} = \beta_0 + (\beta_1 + \gamma_1) t_{ij} \quad (1b).$$

The target of inference is  $\gamma_1$  that represents the mean difference in rate of change among the groups. For the primary language endpoint, treatment efficacy occurs when  $\gamma_1 > 0$ , because language is acquired at a faster rate for TX (cf. Equations 1a and 1b). Therefore, the primary null hypothesis for the analysis is:

$$H_0: \gamma_1 = 0.$$

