## 9.8 Sample Size and Accrual

Estimated required sample size was calculated for the primary endpoint of language. Data from the observational study of was used, and additional estimates of effect size (no raw data) were from an unpublished pre-post randomized clinical trial (RCT). Winarni et al. extracted data from chart reviews for 45 FXS children age 12-50 months. Eleven children were treated with sertraline, and the remainder of 34 were not. Variance components of the random effects and error were estimated and sample size was computed using analytic formulas for LMMs. Recall that in the LMM of Equation 1,  $\gamma_1$  is the difference of the slopes, and it is defined as the proportionate increase of the PL slope,  $\beta_1$ , due to the efficacy of TX (if there is any). We write,  $\gamma_1 = \pi\beta_1$ , where  $\pi$  is the *effect proportion*. For example, if  $\pi = 1$ , Equation 1a shows that the TX slope is twice the PL slope, because  $\beta_1 + \gamma_1 = \beta_1 + (1)\beta_1 = 2\beta_1$ . The analysis used the expressive language and receptive language subscales (age-equivalent scores) of the Mullen Scales of Early Learning. The effect proportion ( $\pi$ ) was estimated considering the on-sertraline group ( $N = 11$ ) as a proxy for TX, and the off-sertraline group ( $N = 34$ ) as a proxy for PL. The effect proportion was also estimated using slope estimates from unpublished data in a RCT of sertraline efficacy. The RCT used a pre-post design over 6 months to study the effect of sertraline versus placebo with FXS children with enrolled age of 24-72 months. Estimates of the effect proportion for the Winarni et al. data were  $\hat{\pi} = 1.27, 2.66$  for expressive language and receptive language respectively, and the estimates from the clinical trial were  $\hat{\pi} = 1.43, 1.52$ . For the analysis, power was set to 80%, and Type I error rate ( $\alpha$ ) was determined as the following. Because this is a proof-of-concept (Phase IIa) proposal with a novel design for a critical population (children with FXS), the  $\alpha$ -level was set to allow for a sensitive detection of efficacy, defined as  $\Delta AIC > 0$  (see statistics section above). It can be shown that  $\Delta AIC = \chi^2_1 - 2$ , so that using  $\chi^2_{1,1-0.16}$  as a critical value for the LRT will allow for detection of  $\Delta AIC > 0$ . In addition to  $\alpha = 0.16$ , sample size was calculated with  $\alpha = 0.10$  because this level is often used in Phase II studies. Figure 3 shows the function of  $\pi$  and  $\alpha$ . A filled circle indicates the required  $N$  for the smallest effect proportion among the studies,  $\min(\hat{\pi}) = 1.43, 1.27$  (expressive, receptive). The figure shows that for the combination of the smallest effect proportion ( $\hat{\pi} = 1.27$ ) and the smallest  $\alpha$ , the required single-arm  $N = 50$  (expressive language). We consider this to be an upper bound on the required sample size, so that a total of  $N = 100$  (50 in each group) should be more than sufficient to detect any magnitude of efficacy (i.e.,  $\Delta AIC > 0$ ). Because of high parental motivation, the dropout rate is anticipated to be very low. However, the  $\alpha = 0.16$  panel of the figure indicates that with total  $N = 100$ , power will still be sufficient to detect  $\Delta AIC > 0$  with as much as 20% dropout ( $100 - 0.2 \times 100 = 80$  or 40 in each group for expressive language).

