#### **10.4.1 Definitions of Adverse Events, Suspected Adverse Drug Reactions & Serious Adverse Events**

##### **10.4.1.1 Adverse Event and Suspected Adverse Drug Reactions**

An adverse event (AE) is any unfavorable and unintended sign (including a clinically significant abnormal laboratory finding, for example), symptom, or disease temporally associated with a

study, use of a drug product or device whether or not considered related to the drug product or device.

Adverse drug reactions (ADR) are all noxious and unintended responses to a medicinal product related to any dose. The phrase “responses to a medicinal product” means that a causal relationship between a medicinal product and an adverse event is at least a reasonable possibility, i.e., the relationship cannot be ruled out. Therefore, a subset of AEs can be classified as suspected ADRs, if there is a causal relationship to the medicinal product.

Examples of adverse events include: new conditions, worsening of pre-existing conditions, clinically significant abnormal physical examination signs (i.e. skin rash, peripheral edema, etc.), or clinically significant abnormal test results (i.e. lab values or vital signs), with the exception of outcome measure results, which are not being recorded as adverse events in this trial (they are being collected, but analyzed separately). Stable chronic conditions (i.e., diabetes, arthritis) that are present prior to the start of the study and do not worsen during the trial are NOT considered adverse events. Chronic conditions that occur more frequently (for intermittent conditions) or with greater severity, would be considered as worsened and therefore would be recorded as adverse events.

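### The individual learning-impairment rule detects only regression, so a child whose learning halts on drug would not be expected to meet it

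*Combined protocol and SAP*

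**What the plan says.** Section 7 (Management of Adverse Experiences) reports learning and memory impairment in preclinical testing of AFQ056 and says the risk will be monitored closely with assessments already in the protocol. Sites watch raw scores on the MSEL and on a scale named VABS-II. Medical Monitor review follows this trigger: "If there is a decrease in raw scores on both measures by 10% incrementally at two consecutive visits where both assessments are administered". The examples in brackets are single intervals: screening to baseline, baseline to month 2, month 2 to month 8, and month 8 to month 16. The next step is: "If there is decrement in these scores without any obvious alternative cause the participant will be withdrawn from the study".

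Section 2.1 (Rationale) says that the decline in standard scores for intelligence and adaptive function with age "is not the results of loss of skills or regression but rather failure to keep pace with the normal rate of intellectual development". It adds that people with fragile X go on acquiring language throughout life, more slowly than others.

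The efficacy model in Section 9.6.1 treats a drug effect as a difference in slope. Efficacy is a positive slope difference "because language is acquired at a faster rate for TX". Section 9.8 sizes the trial on the same quantity: "it is defined as the proportionate increase of the PL slope".

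For the whole trial, Section 6.2.3 gives two stopping routes: three serious adverse events probably or definitely due to drug, or stopping "upon recommendation by the DSMB based on unblinded review of adverse events". Section 10.4.1.1 lists clinically significant abnormal test results as adverse events, "with the exception of outcome measure results, which are not being recorded as adverse events in this trial". After the last blinded assessment, Section 3 says: "All subjects will be dosed with 25 mg BID of unblinded AFQ056 upon completion of the 8 month visit".

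**The concern.** The rule's target and its trigger do not match. If impairment in these children shows as slower gain or no gain, as Section 2.1 suggests, a trigger that needs a fall in raw score is aimed at a different and more extreme event. The plan judges benefit by the rate of gain, while the individual safety rule reacts only to skills already lost.

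At stake is the detection, during the trial, of a risk the protocol itself names, in children aged 3 to 6 for whom Section 9.3 says no extended safety data exist. A child who stopped learning during the blinded period would not be expected to prompt review under this rule before starting open-label drug at month 8. The written DSMB stopping route does not cover the gap, because it refers to adverse events and the relevant scores are not recorded as such.

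**Working it through.** **Inputs from the documents.** Trigger: a 10% fall in raw score on both scales (Section 7). Both scales are given at screening and months 0, 2, 8 and 16 (Section 6.1). Age is at least 36 months at randomisation, and up to 6 years inclusive at screening. I take the upper limit as 84 months, which gives 84 + 4 = 88 months at randomisation. MSEL test-retest reliability is 0.76 to 0.96 (Section 6.3.9). The 10% threshold has no stated derivation, so there is no plan figure to reproduce.

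**Assumptions (not in the documents).** The developmental quotient (DQ) stays constant and raw score is proportional to age-equivalent. The raw-score coefficient of variation (CV) is 20-40%. The MSEL reliability range also applies to Vineland-3. Errors on the two scales are independent, or correlated 0.5. One interval is enough to fire the rule, as the examples in Section 7 suggest.

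**Step 1: complete halt.** Change = (S - S)/S = 0% on both scales, against -10% required. The rule is not met in expectation. This needs none of the assumptions above.

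**Step 2: how much harm gives a 10% fall.** Write g for the child's normal proportional gain over the interval, so g = interval/age at its start. The drug must remove (1 + 0.10/g) times the normal gain.

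| Interval (months) | Age at start (months) | g | Multiple of normal gain |
|---|---|---|---|
| 0-2 | 36 to 88 | 5.6% to 2.3% | 2.8 to 5.4 |
| 2-8 | 38 to 90 | 15.8% to 6.7% | 1.6 to 2.5 |
| 8-16 | 44 to 96 | 18.2% to 8.3% | 1.5 to 2.2 |

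A halt is a multiple of 1.0. By contrast, flat age-equivalents over months 2-8 lower DQ in relative terms by 1 - 38/44 = 13.6% to 1 - 90/96 = 6.3%. The trial's own data would therefore register the halt.

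**Step 3: measurement error, months 2-8.** SD of proportional change = CV x sqrt(2(1 - r)). The range is 0.20 x sqrt(0.08) = 5.7% to 0.40 x sqrt(0.48) = 27.7%. With independent errors, the chance that both scales cross a threshold is the square of the single-scale chance:

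- Halt, 10% rule: Phi(-0.10/SD)^2 = 0.15% to 12.9%.
- Halt, no-gain rule: 0.5^2 = 25%.
- Normal learning, 10% rule: Phi(-(g + 0.10)/SD)^2 = 0% to 7.5%.
- Normal learning, no-gain rule: Phi(-g/SD)^2 = 0% to 16.4%.

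With errors correlated 0.5, the upper ends become 20.4%, 33.3%, 13.7% and 24.4% in the same order.

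**Step 4: extra reviews.** Every 10% fall is also a no-gain, so the extra reviews are the difference between the two rules. At the noisiest setting this is 16.4 - 7.5 = 8.9 per 100 normally learning children. The largest difference falls at intermediate noise: about 10 per 100 with independent errors and about 13 per 100 with correlation 0.5.

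**Step 5: the stricter reading.** If the wording means two successive 10% falls on both scales, a simulation of halted children, with assumed relative error of 2-10% on each score and correlation 0 or 0.5, fires in at most 0.14%. The conclusion holds under either reading.

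**The case against.** Two stronger readings are tempting, and the documents do not support them.

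A reader might infer that the trial measures harm only as lost skills. It does not. The likelihood-ratio test in Sections 9.6.1 and 9.8 compares a one-parameter statistic with a chi-squared quantile, so it also rejects when treated children learn more slowly. MSEL DQ and the Vineland composite are key secondary outcomes compared by arm (Section 9.5.2).

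A reader might also infer that a child who stopped learning would pass every safety check. Several discretionary routes could catch such a child. Section 8 calls for discontinuation if the investigator feels that continuing is detrimental, and sends unclear cases to the protocol investigator, the study team and the medical monitor. The DSMB reviews partially unblinded data and monitors endpoints (Section 9.9). Section 11.3 lets the sponsor, the funding institute, the IRB or the FDA stop the study at any time. Section 9.9 also says DSMB report formats and interim-analysis guidelines will be agreed before enrolment. They are not in these documents, so the absence of a by-arm learning review cannot be shown.

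Other objections also have weight. The withdrawal sentence carries no 10% figure, so read alone it could cover smaller falls, though not a flat score. Section 7 says impairment was not seen in earlier human fragile X trials and that learning improved in the fragile X mouse. Stopping individuals for regression and judging slowing by arm is a defensible division of labour.

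The individual no-gain flag is weak. At the noisiest setting with independent errors, it flags halted and normal children in the ratio 25/16.4 = 1.5, against 12.9/7.5 = 1.7 for the present rule. It gains sensitivity and loses some discrimination. The review is blinded and allocation is 1:1, so flagged children may be on placebo.

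What survives is that no written real-time criterion covers a plateau, for the individual child or in the stated DSMB stopping route.

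**Conclusion.** The point holds in this limited form. The rule written to detect learning impairment detects regression, while the protocol's own account of fragile X points to failure to gain. That a halt gives a 0% expected change, and so does not meet the rule, is free of assumptions. That drug-induced impairment would look like slowing is an inference from Sections 2.1 and 9.6.1, though a direct one.

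The sizes in the working depend on the assumed growth, CVs and error structure. Constant DQ is generous: Section 2.1 reports standard scores declining with age, which would make normal gain smaller, the multiples larger and chance reviews more frequent.

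This is a cheap safety improvement that should be made. The documents give no sign that harm has been missed, and the primary analysis is not affected.

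**What to change.** 1. **Section 6.2.3 (main safeguard).** State that at its scheduled meetings the DSMB also reviews mean change in MSEL and Vineland-3 raw scores by arm, and may recommend stopping for harm on that basis. Section 9.9 already gives it sight of endpoints. Partial slowing can be seen only at this level.

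2. **Section 7.** Keep the 10% rule, stated as one interval in line with its examples, and keep the withdrawal sentence. Add that no gain (change of 0 or less) on both scales from month 2 to month 8 prompts Medical Monitor review, without automatic withdrawal, to decide whether open-label AFQ056 continues.

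3. **Same edit.** Replace VABS-II with Vineland-3, the version in the schedule. Name the scores, for example the sum of MSEL subscale raw scores and the sum of Vineland-3 domain raw scores. Both sets are already entered in the case report forms.

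**Cost.** No new visits or assessments are needed, and no month 8 primary data are lost, because the review follows that visit. On the stated assumptions, about 0-16% of normally learning children would be reviewed at month 8 (up to 24% if errors correlate 0.5). At most about 10 to 13 per 100 of these are extra to the current rule.

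**Limits.** Only about 25-33% of complete halts would be flagged, against about 0.1-20% now. The review comes after blinded exposure has ended, during extension titration, so it can protect only the open-label period.
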